1.4 Preliminary Data

Our team has investigated the feasibility and validity of using fNIRS to measure brain activity in regions associated with influence and persuasion. In an experiment of 41 participants recruited from Amman, Jordan, [name] found that the fNIRS was able to measure several brain regions associated with influence and persuasion, including MPFC as the region most commonly predictive of individual and population-level behavior change in past studies.⁴ Our team has developed an fNIRS protocol manual detailing specific methods for maximizing and standardizing use of equipment that will be updated periodically to reflect best practices and lessons learned.

1.5 Sample Size Justification

We aim to recruit 60 participants. In a recent systematic review of 20 studies that examined persuasive processing and outcomes of the health messages using neurocognitive measures,⁹ the sample size ranged from 14 to 91.⁵ Our primary goal for conducting this experimental study is to examine any preliminary evidence for the efficacy of an open contest approach to develop effective PrEP promotion messages. Effect-size estimates determined through this study will be essential in the design of a larger and fully powered efficacy study that tests intervention effects on PrEP uptake.

1.6 Study Variables

A. Independent Variables, Interventions, or Predictor Variables

Intervention: top three messages developed by an open contest implemented in Baltimore¹.

B. Dependent Variables or Outcome Measures

Brain activity: fNIRS detects the ratio of oxygenated (O₂HB) to deoxygenated (HHB) hemoglobin based on their optical properties, with higher ratios indicating greater neural activity. Neural tissues are relatively transparent to light in the near infrared range between 700-1000 nm, and O₂HB and HHB reflect distinct wavelengths in this range. By modulating light at different wavelengths, emitting the light on the skin-exposed areas of the cranium, and detecting that light, fNIRS measures the blood oxygenation level dependent signal (BOLD) like fMRI. Because the photons reflected from neural tissue follow a reliable 'banana-shaped' path, photodetectors can be used to measure this on the scalp. By measuring the amount of absorbed light directed at the neural tissue, we can measure the amount of O₂HB and HHB present in a region of the brain at a given time and draw inferences about the level of neural activity.

PrEP-related beliefs, willingness, behavioral intention, and behavior:

All questions will be asked to participants at baseline (only to individuals aware of PrEP), at the in-person visit after reviewing all messages, and at the 30-day follow up, except questions on PrEP action and initiation, which will only be asked at the 30-day follow up.

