1.0 Research Design

1.1 Purpose/Specific Aims

A. Objectives

This study will examine the feasibility, acceptability, and utility of neuroimaging technique to evaluate pre-exposure prophylaxis (PrEP) promotion messages for men who have sex with men (MSM) at risk of HIV in Baltimore, MD. The **specific aim** is:

Evaluate the effectiveness of PrEP promotion messages developed via a crowdsourcing open contest¹ by assessing neural bases of persuasion.

B. Hypotheses / Research Question(s)

This is an experimental study using neuroimaging technique to assess the persuasiveness of messages developed by a crowdsourcing open contest approach the study team conducted previously.

We hypothesize that, compared with participants viewing messages developed by a social marketing approach:

- H1. Participants viewing top messages developed via open contests will show higher brain activation in the Medial Prefrontal Cortex (MPFC) regions.
- H2. A greater proportion of participants viewing top messages developed via open contests will report increased willingness and behavioral intention to take PrEP.
- H3. A greater proportion of participants viewing top messages developed via open contests will report taking PrEP action and initiation during 30-day follow up.
- H4. Brain activation in the MPFC regions is significantly more correlated with PrEP action and initiation than self-reported message effectiveness.

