1.9 Data Collection

A. Primary Data Collection

▪ **Location:**

Baseline survey: in-person data collection in a private office

Neuroimaging data and post-messaging survey: in-person data collection at the private office in a community partner/community-based organization.

30-day follow up survey: online or over the phone

• **Process of Data Collection:**

Once an individual is screened eligible, he will provide an informed consent and complete a baseline survey. An in-person visit will be scheduled, roughly a week after completing the baseline survey. During the in-person visit, participants in each group will view multiple messages on a computer screen while brain activity is recorded. After completing all messages, participants will answer questions on perceived effectiveness of the messages, self-efficacy, and willingness and behavioral intention to use PrEP. Semi-structured questions on the acceptability of fNIRS will also be asked. All participants will complete a 30-day follow up by phone call or online to assess any behavioral change.

▪ **Timing and Frequency:**

Baseline survey, in-person visit/one week after completing the baseline survey, 30-day follow up

▪ **Procedures for Audio/Visual Recording:**

N/A.

▪ **Study Instruments:**

PrEP-related beliefs, willingness, behavioral intention, and behavior:

All questions will be asked to participants at baseline (only to individuals aware of PrEP), at the 2nd visit after reviewing all messages, and at the 30-day follow up, except questions on PrEP action and initiation, which will only be asked at the 30-day follow up.

Self-efficacy: Participants will be asked, on a 4-point Likert scale ranging from strongly disagree to strongly agree, to rate their agreement with the statement “I feel confident I could take PrEP as prescribed.”

Willingness: Participants will be asked, “Suppose that PrEP is at least 90% effective in preventing HIV when taken daily. How likely would you be to take PrEP if it were available for free?” with responses ranging from “I would definitely take it” to “I would definitely not take it.”⁶⁰

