Behavioral Intention: We will assess behavioral intentions to actually begin PrEP based on a real-world situation. To do this, participants will be asked, “PrEP is currently available with a prescription from your doctor and research has shown that a majority of insurance companies cover most or all of the costs of PrEP. Do you plan to begin PrEP?” Response options range from “Yes, I will definitely begin taking PrEP” to “No, I definitely will not begin taking PrEP.”

PrEP action and initiation: Items include “Have you spoken with a provider about PrEP during the past 30 days?” and “Have you started taking PrEP during the past 30 days?”

Message-related measures:

All questions will be asked after participants finish reviewing all messages during the in-person visit.

Perceived effectiveness: Participants will be asked, on a 4-point Likert scale ranging from strongly disagree to strongly agree, to rate their agreement that the message is believable, new, unconvincing, important to them, helps them feel confident about using PrEP, would help their friends use PrEP, put thoughts in their mind about using PrEP.

Baseline survey

Socioeconomic status: We will collect data on age, highest level of education attained, housing, employment history, health insurance status, access to health care, sources and amount of personal and household income,

Sexual identity: We will use a question from our previous study which asks participants to choose from heterosexual/straight, bisexual, homosexual/gay/same-gender loving, or not sure/questioning.

Sexual history: number of sex partners, sex of the partners, condom use in the past 90 days

Social media use: Types of social media sites used for socializing, seeking sex partners, and seeking health-related information.

HIV testing history

- **Ethnographic Studies, Interviews, Or Observation:**

N/A

- **Subject Identifiers:**

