4.0 Subject Considerations

4.1 Subject Selection and Enrollment Considerations

A. Method to Identify Potential Subjects

Participants will be recruited from a range of settings, including venue based outreach at community partner sites (CBOs, health clinics), street outreach, printed and online advertisements (CBO websites or Facebook pages), and word of mouth referral.

B. Recruitment Details

Recruitment staff will assess willingness of the establishment gatekeepers to permit recruitment activities. Recruitment of participants will be conducted by research staff who will receive extensive training in ethical guidelines regarding professional conduct and in how to approach and engage potential study participants. Staff will be asked to sign a pledge to protect respondent privacy and confidentiality. Recruitment staff will have a cellular phone to contact the study PI and/or security in the event that they are concerned about their safety. Each person approached will be given a project recruitment flyer that provides basic information regarding the study. Potential participants will be given information about the nature of the study, the time involved, and informed that they will be financially reimbursed for their time. In order to reduce potential embarrassment or inadvertent disclosure of HIV or sexual behaviors the script will include the comment, "If this doesn't apply to you, please give it to someone you know."

C. Subject Screening

Participants will provide verbal consent to be screened for the study. Eligible participants will be asked to provide written consent, complete a baseline survey and scheduled for the baseline visit.

- Inclusion Criteria**

Key inclusion criteria in this study are 1) 18 years and older; 2) biological male sex at birth; 3) sexually active with men in the past 6 months; 4) never taken PrEP; 5) HIV negative; 6) reside in Baltimore City or surrounding counties; and 7) meet one of the criteria for being an appropriate PrEP candidate¹: a) in a relationship with a partner not known to be HIV-negative, b) were in a nonmonogamous relationship, c) had any condomless anal sex with a casual male partner regardless of status in the prior 6 months, or d) had a positive STI diagnosis within the prior 6 months.

- Exclusion Criteria**

N/A

D. Privacy Protections

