6.0 Data Management Plan

6.1 Data Analysis

Our primary aim in this study is to assess the effectiveness of PrEP promotion messages developed via open contest by assessing brain activation in the regions associated with persuasion (i.e., Medial Prefrontal Cortex (MPFC)), and any changes in participants' PrEP willingness, behavioral intention, initiation, and action in 30-day follow up. We will first assess whether the randomization has worked by comparing baseline demographic and confounding variables of participants in each arm using Fisher's exact test for dichotomous variables, analysis of variance (ANOVA) tests for nominal variables and normally distributed continuous variables, and Wilcoxon signed-rank tests for non-normally distributed continuous variables, with statistical significance determined at alpha=0.05. Any variable for which randomization did not result in equal proportions in each arm will be incorporated into the multivariate models as a potential confounding variable.

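### PrEP action has no baseline measure and no entry criterion sets it to zero, so continuing provider contact cannot be told from contact the messages prompted; H3 loses precision and H4 can be confounded

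*Combined protocol and SAP*

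**What the plan says.** Section 1.6 B lists the PrEP measures taken at baseline, at the message visit and at follow-up, "except questions on PrEP action and initiation, which will only be asked at the 30-day follow up". Section 1.9 repeats the rule: "at the 2nd visit after reviewing all messages, and at the 30-day follow up, except questions on PrEP action and initiation". At baseline the PrEP questions go only to men who have heard of PrEP.

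The two items are "Have you spoken with a provider about PrEP during the past 30 days" (action) and "Have you started taking PrEP during the past 30 days" (initiation).

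The inclusion criteria in 4.1 C contain "4) never taken PrEP; 5) HIV negative; 6) reside in Baltimore City or surrounding counties". They do not mention earlier discussion of PrEP with a provider, and there are no exclusion criteria. Recruitment under 4.1 A includes "venue based outreach at community partner sites (CBOs, health clinics". The baseline survey in 1.9 covers access to health care but lists no question on a previous PrEP conversation.

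Section 6.1 opens by describing an aim to assess "any changes in participants' PrEP willingness, behavioral intention, initiation, and action in 30-day follow up". Its inferential paragraph then analyses action and initiation as yes/no at 30 days and keeps increase from baseline for willingness and intention. H4 in 1.1 B reads: "Brain activation in the MPFC regions is significantly more correlated with PrEP action and initiation than self-reported message effectiveness".

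**The concern.** For initiation, the eligibility rule supplies the missing baseline: every participant starts at zero. Nothing does this for action. A man who was already discussing PrEP with a provider is eligible, and recruitment in clinics makes such men plausible participants. If he has another such conversation before follow-up, his answer is the same as that of a man who was prompted by the messages.

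The consequences differ by hypothesis. H3 compares randomised arms, so background contact is expected equally in both; the cost is dilution, plus chance imbalance that nobody can check. H4 relates brain response to later behaviour across individuals, where randomisation gives no protection. Section 1.2 describes MPFC activity as reflecting how far a message fits a person's self-concept. Men already pursuing PrEP might show more of it and also be likelier to report contact. Part of the correlation would then reflect engagement that predates the scan. The covariate rule in 6.1 does not help, because it admits only measured variables that differ between arms.

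**Working it through.** The plan states no event rate, effect size or power for action, so there is no figure to reproduce. All rates in steps 2 and 3 are assumptions.

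**1. Recall window.** Section 1.3 A puts the message visit roughly a week after the baseline survey. Section 1.9 lists the 30-day follow-up after that visit but does not say from which day the 30 days run.
- Counted from the message visit, with the survey on time: 0 of 30 days precede exposure.
- Counted from the baseline survey: 7/30 = 23% precede exposure (5/30 = 17% to 10/30 = 33% for gaps of 5 to 10 days).

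**2. H3.** Take 30 per arm, two-sided alpha 0.05 and the normal approximation for two proportions. Let a share b in each arm answer yes regardless of the messages, and let the messages produce yes in 5% v 25% of the rest. The arm rates are b + (1 - b) x 0.05 and b + (1 - b) x 0.25, so the difference is 0.20 x (1 - b).

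| b | Rates | Difference | Power |
|---|---|---|---|
| 0 | 5.0% v 25.0% | 0.20 | 59% |
| 10% | 14.5% v 32.5% | 0.18 | 37% |
| 20% | 24.0% v 40.0% | 0.16 | 26% |
| 30% | 33.5% v 47.5% | 0.14 | 19% |

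Background contact shrinks the contrast but creates no expected difference between arms. A baseline item would recover only part of the lost power.

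**3. H4.** Let b be the share already engaged, p1 and p0 the chance of a yes at 30 days with and without earlier engagement, and d the shift in MPFC response (in SD) among the engaged. Assume no other link between MPFC response and action. With p = b p1 + (1 - b) p0,

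r = d (p1 - p0) b(1 - b) / sqrt{ p(1 - p) [1 + d² b(1 - b)] }.

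Central case: b = 0.20, p1 = 0.60, p0 = 0.15, so p = 0.12 + 0.12 = 0.24, and half of all yes answers come from the engaged.
- d = 0.5: 0.036 / sqrt(0.1824 x 1.04) = 0.083.
- d = 1: 0.072 / sqrt(0.1824 x 1.16) = 0.157.

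For b from 10% to 30%, d of 0.5 or 1, and (p1, p0) of (0.60, 0.15), (0.50, 0.20), (0.50, 0.10) or (0.30, 0.10), r runs from 0.03 to 0.19.

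H4 concerns the difference between two correlations with the same outcome, so self-rated effectiveness needs the same calculation. In the central case:
- both shifted by 1 SD: 0.157 - 0.157 = 0;
- MPFC by 1 SD, self-rating by 0.5 SD: 0.157 - 0.083 = 0.074;
- MPFC only, by 1 SD: 0.157.

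For scale, the standard error of one correlation at n = 60 is about 1/sqrt(57) = 0.13.

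**The case against.** The strongest reply is the recall period. A reader might infer that any provider contact before the trial counts as an outcome. The documents do not support that: the item covers only the past 30 days, so earlier contact enters only if it continues or recurs, is misdated, or falls before exposure because the window starts too early. This stands and narrows the point. It does not remove it, since the item cannot separate a continuing conversation from a new one.

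A reader might also infer from the opening of 6.1 that a primary change analysis of action is planned and cannot be computed. The inferential paragraph defines action by status at 30 days, and H3 is worded in the same way. No planned analysis needs a change score, so this is a matter of wording.

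On H4, prior engagement may raise self-rated effectiveness too; one of its items asks whether the message matters to the participant personally. Equal influence cancels in the difference, and a stronger influence on self-rating would work against H4. This also stands: H4 can be confounded, but it is not shown to be. Because prior contact is not recorded, the plan cannot tell which case applies.

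Baseline willingness, intention and access to health care are partial proxies. The first two are missing for men unaware of PrEP, and none records contact. It is also fair that the study seeks only preliminary evidence and that 6.1 names no analysis for H4 at all, which is the larger gap. Still, 1.5 intends the effect-size estimates to inform a larger trial, so a diluted estimate for action would carry forward.

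**Conclusion.** The point holds in a limited form. Action lacks both a baseline measure and an entry criterion that sets it to zero, and the start of its 30-day window is unstated. Continuing contact can therefore be scored as a response to the messages.

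H3 is not biased in expectation; it loses precision. In the assumed scenario, a 20% background rate cuts power from 59% to 26%. H4 may be biased by an amount between about zero, with equal influence on both predictors, and roughly 0.03-0.19, with influence on MPFC alone. At the top of that range the bias is somewhat larger than one standard error of a single correlation. The documents supply none of these rates, and the higher ones presume that provider conversations often repeat from month to month.

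A reader might also want to convert the variance explained by baseline contact into participants saved. That conversion belongs to a linear model and does not carry over to the logit model in 6.1. The case for change rests on interpretability at very low cost.

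**What to change.** 1. Add two yes/no questions to the baseline survey for every participant: ever spoken with a provider about PrEP, and spoken with one in the past 30 days. Score men unaware of PrEP as no. The first is needed because a 30-day item alone misses older contact that could still make the messages self-relevant.
2. Word the follow-up action item as since the study visit, and state in 1.9 that the 30 days run from the message visit.
3. Prespecify baseline contact as a covariate for action in H3. In H4, adjust both correlations for it. Report action among men with no prior contact as a sensitivity analysis.
4. In 6.1, describe action and initiation as status at 30 days, in line with the inferential paragraph. Initiation needs no baseline item.

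The cost is two short questions in an existing survey and one covariate. The questions may themselves prompt some men to speak to a provider, but they precede randomisation, so this is expected equally in both arms. Events will be few: at the assumed 24%, 0.24 x 60 is about 14, so the model should carry little beyond this covariate. Contact first made in the week between the baseline survey and the visit would stay unrecorded; repeating the question at the visit before randomisation would close that gap.

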1.7 Drugs/Devices/Biologics

N/A.

1.8 Primary Specimen Collection

N/A.

1.9 Data Collection

A. Primary Data Collection

▪ **Location:**

Baseline survey: in-person data collection in a private office

Neuroimaging data and post-messaging survey: in-person data collection at the private office in a community partner/community-based organization.

30-day follow up survey: online or over the phone

• **Process of Data Collection:**

Once an individual is screened eligible, he will provide an informed consent and complete a baseline survey. An in-person visit will be scheduled, roughly a week after completing the baseline survey. During the in-person visit, participants in each group will view multiple messages on a computer screen while brain activity is recorded. After completing all messages, participants will answer questions on perceived effectiveness of the messages, self-efficacy, and willingness and behavioral intention to use PrEP. Semi-structured questions on the acceptability of fNIRS will also be asked. All participants will complete a 30-day follow up by phone call or online to assess any behavioral change.

▪ **Timing and Frequency:**

Baseline survey, in-person visit/one week after completing the baseline survey, 30-day follow up

▪ **Procedures for Audio/Visual Recording:**

N/A.

▪ **Study Instruments:**

PrEP-related beliefs, willingness, behavioral intention, and behavior:

All questions will be asked to participants at baseline (only to individuals aware of PrEP), at the 2nd visit after reviewing all messages, and at the 30-day follow up, except questions on PrEP action and initiation, which will only be asked at the 30-day follow up.

Self-efficacy: Participants will be asked, on a 4-point Likert scale ranging from strongly disagree to strongly agree, to rate their agreement with the statement “I feel confident I could take PrEP as prescribed.”

Willingness: Participants will be asked, “Suppose that PrEP is at least 90% effective in preventing HIV when taken daily. How likely would you be to take PrEP if it were available for free?” with responses ranging from “I would definitely take it” to “I would definitely not take it.”⁶⁰

Behavioral Intention: We will assess behavioral intentions to actually begin PrEP based on a real-world situation. To do this, participants will be asked, “PrEP is currently available with a prescription from your doctor and research has shown that a majority of insurance companies cover most or all of the costs of PrEP. Do you plan to begin PrEP?” Response options range from “Yes, I will definitely begin taking PrEP” to “No, I definitely will not begin taking PrEP.”

PrEP action and initiation: Items include “Have you spoken with a provider about PrEP during the past 30 days?” and “Have you started taking PrEP during the past 30 days?”

Message-related measures:

All questions will be asked after participants finish reviewing all messages during the in-person visit.

Perceived effectiveness: Participants will be asked, on a 4-point Likert scale ranging from strongly disagree to strongly agree, to rate their agreement that the message is believable, new, unconvincing, important to them, helps them feel confident about using PrEP, would help their friends use PrEP, put thoughts in their mind about using PrEP.

Baseline survey

Socioeconomic status: We will collect data on age, highest level of education attained, housing, employment history, health insurance status, access to health care, sources and amount of personal and household income,

Sexual identity: We will use a question from our previous study which asks participants to choose from heterosexual/straight, bisexual, homosexual/gay/same-gender loving, or not sure/questioning.

Sexual history: number of sex partners, sex of the partners, condom use in the past 90 days

Social media use: Types of social media sites used for socializing, seeking sex partners, and seeking health-related information.

HIV testing history

- **Ethnographic Studies, Interviews, Or Observation:**

N/A

- **Subject Identifiers:**

We will collect identifiable information, including name, email address and phone numbers, which will be kept in secured Participation Database during the enrollment. All identifiable information about each participant is kept separate from the participant's study ID number. We maintain a master list that links study ID number and identifier. The linkage between study ID number and identifiable information will be encrypted and saved on a password-protected server. The master list must be retained in order to plan subsequent stages of follow up, but it will be destroyed at the completion of the study.

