Next, we will conduct primary inferential analyses to compare a) the level of neural activity in MPFC, b) increase in willingness and behavioral intention to take PrEP between baseline and 30-day follow up (yes/no), and c) PrEP action and initiation at 30-day follow up (yes/no) among participants in the three conditions. fNIRS detects the ratio of oxygenated (O₂HB) to deoxygenated (HHB) hemoglobin based on their optical properties, with higher ratios indicating greater neural activity. By modulating light at different wavelengths, emitting the light on the skin-exposed areas of the cranium, and detecting that light, fNIRS measures the blood oxygenation level dependent signal (BOLD) similar to fMRI. Because the photons reflected from neural tissue follow a reliable 'banana-shaped' path, photodetectors can be used to measure this on the scalp. By measuring the amount of absorbed light directed at the neural tissue, we can measure the amount of O₂HB and HHB present in a region of the brain at a given time and draw inferences about the level of neural activity. The level of brain activation for the top message condition compared to references will be evaluated using pairwise comparison. For the binary outcome measures, increase in willingness and behavioral intention to take PrEP and PrEP action and initiation, we will first compare proportions by conditions separately for each measurement period using standard bivariate analytic techniques such as Spearman rank-order correlations, odds ratios, and Fisher's exact test. Then we will employ generalized linear mixed

models (GLMM) to evaluate the effectiveness of top messages developed via open contest. GLMM permits us to measure the fixed effect of the top messages developed via open contest on neural activity, willingness and behavioral intention to take PrEP, and PrEP action and initiation, while allowing a random effect that accounts for within-person correlation. Given the binary nature of two primary outcomes, we will specify a logit link function for our GLMM models. Comparisons of characteristics of participants who are lost to follow-up to those who are evaluated will be conducted to assess for systematic patterns that could influence results.

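### The willingness and intention outcome is an increase from baseline, but men unaware of PrEP are not asked those items at baseline, so it is undefined for them

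*Combined protocol and SAP*

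**What the plan says.** H2 in Section 1.1 concerns increased willingness and intention to take PrEP and sets no time window. Section 6.1 supplies one. Among its primary comparisons it lists "increase in willingness and behavioral intention to take PrEP between baseline and 30-day follow up (yes/no".

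The item schedule is in Section 1.9 (Study Instruments): "All questions will be asked to participants at baseline (only to individuals aware of PrEP". Section 1.6 gives the same rule. The later administrations, at the in-person visit and at day 30, carry no such restriction. Section 1.9 also fixes the order at the visit: "After completing all messages, participants will answer questions on perceived effectiveness of the messages, self-efficacy, and willingness and behavioral intention to use PrEP".

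The inclusion criteria in Section 4.1 refer to PrEP use, not PrEP awareness: "4) never taken PrEP; 5) HIV negative; 6) reside in Baltimore City or surrounding counties". Apart from these, the criteria cover age, sex at birth, recent sex with men and PrEP candidacy. There are no exclusion criteria.

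On missing information, Section 6.1 offers one step: "Comparisons of characteristics of participants who are lost to follow-up to those who are evaluated will be conducted".

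**The concern.** A change from baseline needs a baseline value. For men unaware of PrEP the plan chooses not to collect one, and their first answer follows exposure to the messages, so it cannot stand in. The gap is created by the questionnaire and not by dropout, and comparing men lost to follow-up with the rest does not address it.

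Three things are at stake. The first is precision in a sample of 60. The second is scope: an analysis of aware men says nothing about men who had not heard of PrEP. The third is analyst discretion. With no rule, someone must decide after the data are in whether to exclude unaware men, use their later levels, or assign them a code. These choices answer different questions, and Section 1.5 says the study's effect-size estimates are to inform the design of a larger trial.

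**Working it through.** The plan states no figure for this outcome, so there is none to reproduce. The main point follows from setting the sections side by side.

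1. The outcome is an increase from baseline to day 30 (Section 6.1).
2. The baseline term exists only for aware men (Sections 1.6 and 1.9).
3. Unaware men are eligible (Section 4.1) and are randomised at the second visit, roughly a week after the baseline survey (Section 1.3).
4. The outcome is therefore undefined for every unaware man, and no section gives a substitute value, coding rule or analysis set.

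**Inputs for the size.** N = 60 completers (Section 4.3), split equally into 30 per arm (Section 1.3). The unaware share *u* is not in the documents; 10, 25 and 40% are assumptions. The 40% response per arm is also assumed.

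**If unaware men are left out:**

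- Evaluable n = 60(1 − u)
- SE inflation = 1/√(1 − u)
- 95% half-width = 1.96 × √(2 × 0.4 × 0.6 / (n/2))

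| u | Evaluable n | SE factor | Half-width (points) |
|---|---|---|---|
| 0 | 60 | 1.00 | 24.8 |
| 10% | 54 | 1.05 | 26.1 |
| 25% | 45 | 1.15 | 28.6 |
| 40% | 36 | 1.29 | 32.0 |

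As a second scale, take increase rates of 20% v 50% (assumed) and two-sided alpha 0.05. Exact power of Fisher's test is 60% with 60 men, 55% with 54 and 36% with 36.

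**If unaware men were coded as no increase.** The plan does not propose this; it shows how much the choice can matter. Assume 50% v 30% among aware men, a difference of 20 points.

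- Average reported difference = (1 − u) × 20 = 18, 15 or 12 points.
- Chance imbalance: with k = 6, 15 or 24 unaware men split at random over two arms of 30, the count in one arm has SD √(30 × (k/60) × (1 − k/60) × (30/59)) = 1.17, 1.69 or 1.91.
- Each unaware man moved between arms shifts the expected difference by 100 × (0.5 + 0.3)/30 = 2.67 points, which gives an SD of 3.1, 4.5 or 5.1 points.

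The shrinkage therefore holds on average, not in every sample.

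**The case against.** The strongest reply is that Section 6.1 already contains a way round. It says "we will first compare proportions by conditions separately for each measurement period", and its mixed model addresses "willingness and behavioral intention to take PrEP, and PrEP action and initiation, while allowing a random effect that accounts for within-person correlation". A single yes/no change per man has no within-person correlation to model, so this wording suggests repeated levels, in which case unaware men's visit and day-30 answers could enter. That is a fair reading of part of the section. But the same section defines the outcome as an increase, lists it that way among the binary measures, and never says the levels are to be used. The route is available but not chosen.

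The unaware share may also be small. Men are screened on PrEP history and candidacy and told about the study before the baseline survey, and the plan does not define awareness. This stands: the size is unknown, and near zero the loss is negligible. The rule in Sections 1.6 and 1.9 nevertheless anticipates some unaware men.

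Not asking unaware men can be a deliberate way to avoid priming. That is defensible, but it still needs an outcome that works without the answers.

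A floor value could be assigned, since a man who has not heard of PrEP has no plan to begin it. This would make intention computable, but it is less convincing for willingness, which is a hypothetical question. It is one more choice that needs to be made in advance.

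Finally, this is a preliminary study whose intervals are wide anyway. True, and it limits the severity. It does not remove the need for an outcome that can be computed in everyone randomised and followed.

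**Conclusion.** The concern holds. As written, the H2 outcome cannot be computed for men unaware of PrEP, and the plan does not say what to do with them. That conclusion needs no outside figure.

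The size does. Under the assumed unaware shares of 10 to 40%, between 6 and 24 of 60 men drop out of the comparison and the half-width widens by roughly 1 to 7 points. Any loss to follow-up at day 30 would add to this. Excluding these men leaves a valid randomised comparison, so the harm is lost precision, a narrower population and an analysis left open, not bias between arms. H1, H3 and H4 do not use the baseline items. The point should be fixed, but it does not undermine the trial as a whole.

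**What to change.** Choose one of two changes.

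**Option 1: ask everyone.** At baseline, give each participant a one-sentence neutral description of PrEP, ask willingness and intention of all, and record awareness as a separate item. This keeps the increase outcome. The cost is one survey sentence plus the review in Section 6.3 (IRB review and notice to the NIH Project Officer). The downside is slight early exposure of unaware men in both arms about a week before the messages, which may affect the rating of whether the message is new.

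**Option 2: change the outcome.** Use this if the survey is locked or priming is to be avoided.

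- Compare day-30 responses between arms in all randomised men with follow-up, adjusting for baseline score (set to a constant where not asked) and an awareness indicator.
- State that this replaces the increase as the quantity estimated, and name the cut-off or ordinal model for the graded responses, which Section 6.1 does not give.
- Report the increase among aware men as secondary, with evaluable numbers by arm.
- Do not code unaware men as showing no increase.

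Option 2 needs no new question. It does need the awareness answer that routes the survey to be kept in the dataset; the baseline variables described in Section 1.9 do not include it. At an assumed 40% response per arm, it keeps the 25-point half-width before adjustment. As an amendment to the analysis section, it goes through the same review and notice.
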